11.2.9. Hospitalization or Prolonged Hospitalization

Any AE that results in hospitalization or prolonged hospitalization should be documented and reported as an SAE (per the definition of SAE in Section 11.1.3), except as outlined below.

The following hospitalization scenarios are **not considered** to be SAEs:

- Hospitalization for respite care
- Standard procedure for protocol therapy administration; however, hospitalization or prolonged hospitalization for a complication of therapy administration will be reported as an SAE
- Routine treatment or monitoring of the studied indication not associated with any deterioration in condition
- Administration of blood or platelet transfusion as routine treatment of studied indication; however, hospitalization or prolonged hospitalization for a complication of such transfusion remains a reportable SAE
- A procedure for protocol/disease-related investigations (eg, surgery, scans, endoscopy, sampling for laboratory tests, bone marrow sampling); however, hospitalization or prolonged hospitalization for a complication of such procedures remains a reportable SAE
- Hospitalization or prolongation of hospitalization for technical, practical, or social reasons, in absence of an AE
- A procedure that is planned (ie, planned prior to start of treatment on study); must be documented in the source document and the eCRF; hospitalization or prolonged hospitalization for a complication remains a reportable SAE
- An elective treatment of or an elective procedure for a pre-existing condition, unrelated to the studied indication, that has not worsened from baseline

11.2.10. Overdose or Incorrect Administration

Study treatment overdose is the accidental or intentional use of the drug in an amount higher than the dose being studied. An overdose or incorrect administration of study treatment is not an AE unless it results in untoward medical effects.

Any study treatment overdose or incorrect administration of study treatment should be noted on the Study Drug Administration eCRF.

All AEs associated with an overdose or incorrect administration of study treatment should be recorded on the Adverse Event eCRF. If the associated AE fulfills serious criteria, the event should be reported to the Sponsor by the Investigator within 24 hours after learning of the event.

11.3. Other Potential Risks

11.3.1. Leukoencephalopathy

Leukoencephalopathy is a potential risk associated with AG-120 treatment based on clinical safety findings observed across the AG-120 clinical development program. Progressive multifocal leukoencephalopathy (PML) and posterior reversible encephalopathy syndrome (PRES), both Grade 3 SAEs, have each been reported in 1 subject with underlying hematologic malignancies.

The signs and/or symptoms of PML may begin gradually, usually worsen rapidly, and vary depending on which part of the brain is infected. Signs and symptoms may include difficulty with walking and other movements, progressive weakness, decline in mental function, visual field deficits, and speech and language disturbances. Rarely, headaches and seizures occur. Subjects should be monitored for onset of signs or symptoms suggestive of PML. Diagnostic evaluations may include consultation with a neurologist, MRI of the brain, lumbar puncture, and/or brain biopsy as clinically warranted. The Investigator should immediately contact the Study Medical Monitor when PML is a suspected or confirmed diagnosis. Treatment with AG-120 should be suspended in the setting of suspected PML and permanently discontinued in subjects with confirmed PML.

Posterior reversible encephalopathy syndrome is a rare clinico-radiological neurological syndrome ([Linda and von Heijne, 2015](#)). Clinical characteristics may include sub-acute onset of headache, hypertension, seizures, altered mental status, visual disturbances, and occasionally other focal neurological signs. Radiologically, signs of vasogenic edema are usually seen bilaterally in the white matter of the parieto-occipital lobes, but changes can also be seen in frontal and temporal lobes, brainstem, cerebellum, and in cortical as well as deep gray matter. Subjects should be monitored for onset of neurological signs and/or symptoms that are clinically associated with PRES. Diagnostic evaluations may include consultation with a neurologist, MRI of the brain, and other recognized standard of care measures as clinically warranted. Additionally, the Investigator should consult with the Study Medical Monitor for management guidelines to be utilized in the setting of suspected or confirmed PRES.

Refer to Section 6.5.8.1 (PML) and Section 6.5.8.2 (PRES) in the AG-120 Investigator's Brochure for further details on these events.

11.3.2. Sensorimotor Neuropathy/Polyneuropathy

Sensorimotor neuropathy/polyneuropathy is a potential risk associated with AG-120 treatment based on safety findings observed across the AG-120 clinical development program. Guillain-Barre syndrome (Grade 2 SAE in 1 subject; Grade 3 SAE in 1 subject, both with underlying hematologic malignancies) and lumbosacral plexopathy (Grade 2 SAE in 1 subject with underlying hematologic malignancy) are rare, serious syndromes that affect the central and peripheral nervous systems.

Subjects should be monitored for onset of new signs or symptoms of motor and/or sensory neuropathy such as unilateral or bilateral weakness, sensory alterations, or paresthesia. If a subject experiences signs or symptoms suggestive of sensorimotor neuropathy, Guillain-Barre syndrome, or lumbosacral plexopathy, diagnostic evaluation may include a consultation with a

neurologist, lumbar puncture, and electromyography. The Investigator should immediately contact the Study Medical Monitor when Guillain-Barre syndrome is a suspected or confirmed diagnosis. AG-120 should be permanently discontinued in subjects with a confirmed diagnosis of Guillain-Barre syndrome. Refer to Section 6.5.6 (Sensorimotor Neuropathy/Polyneuropathy) in the AG-120 Investigator's Brochure for further details on these events.

11.4. Pregnancy Reporting

Pregnancy is neither an AE nor an SAE, unless a complication relating to the pregnancy occurs (eg, spontaneous abortion, which may qualify as an SAE).

Pregnancies and suspected pregnancies (including a positive pregnancy test regardless of age or disease state) of a female subject or partner of a male subject occurring while the subject is on study treatment, or within 28 days of the subject's last dose of study treatment, are considered immediately reportable events. If a female partner of a male subject taking investigational product becomes pregnant, the male subject taking study treatment should notify the Investigator, and the pregnant female partner should be advised to call her healthcare provider immediately. In pregnant female subjects, study treatment is to be discontinued immediately and the subject instructed to return any unused study drug to the Investigator. The pregnancy, suspected pregnancy, or positive pregnancy test must be reported immediately using the pregnancy reporting form. The Investigator must follow-up and document the course and outcome of all pregnancies even if the subject was discontinued from the study or if the study has finished. The female subject or partner of a male subject should receive any necessary counseling regarding the risks of continuing the pregnancy and the possible effects on the fetus. Monitoring should continue until conclusion of the pregnancy.

All outcomes of pregnancy (from a female subject or the sexual partner of a male subject) must be reported by the Investigator to the Sponsor or Medical Monitor on a pregnancy reporting form within 28 days after he/she has gained knowledge of the delivery or elective abortion.

Any SAE that occurs during pregnancy must be recorded on the SAE report form (eg, maternal serious complications, spontaneous or therapeutic abortion, ectopic pregnancy, stillbirth, neonatal death, congenital anomaly, or birth defect) and reported within 24 hours in accordance with the procedure for reporting SAEs.

Females of reproductive potential must have a negative serum pregnancy test prior to the start of therapy, or a confirmation from an obstetrician in case of equivocal serum pregnancy results. Women of reproductive potential, as well as fertile men with partners who are female with reproductive potential, must agree to use 2 effective forms of contraception (including at least 1 barrier form) from the time of giving informed consent throughout the study and for 90 days (both females and males) following the last dose of study drug. Females of reproductive potential are defined as sexually mature women who have not undergone a hysterectomy or bilateral oophorectomy or who have not been naturally postmenopausal (ie, who have not menstruated at all) for at least 24 consecutive months (ie, has had menses at any time in the preceding 24 consecutive months).

Males with partners who are female with reproductive potential must agree that they or their partners will use 2 effective forms of contraception (including at least 1 barrier form) when

engaging in reproductive sexual activity throughout the study and will avoid conceiving for 90 days after the last dose of study treatment.

Effective forms of contraception are defined as hormonal oral contraceptives, injectables, patches, intrauterine devices, intrauterine hormone-releasing systems, bilateral tubal ligation, condoms with spermicide, or male partner sterilization. Please refer to Section 9.13.4 for further details on potential drug-drug interactions with hormonal contraceptives.

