11. ADVERSE EVENTS

Monitoring of AEs will be conducted throughout the study (once subjects have received study drug); SAEs that are assessed as related to study treatment that occur >28 days post treatment also are to be reported. All AEs should be monitored until they are resolved or are clearly determined to be due to a subject's stable or chronic condition or intercurrent illness(es).

Adverse Event Reporting Period

Investigators will seek information on AEs at each subject contact, as outlined below. All AEs, whether reported by the subject or noted by study personnel, will be recorded in the subject's medical record and on the Adverse Event eCRF.

- After informed consent has been obtained but prior to initiation of study drug, only SAEs caused by a protocol-mandated intervention should be reported (eg, SAEs related to invasive study procedures such as biopsies).
- After initiation of study drug, all AEs and SAEs regardless of attribution will be collected at every visit until 28 days following the last administration of study treatment or until study discontinuation/termination or until initiation of subsequent anticancer therapy, whichever occurs first. Subjects will be assessed at the Follow-Up Visit to determine if any new AEs have occurred. After this period, Investigators should report only SAEs that are considered to be related to study treatment (AG-120/placebo).

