11.5. Follow-up of Subjects After Adverse Events

11.5.1. Investigator Follow-Up

The Investigator should follow each AE until the event has resolved to baseline grade or better, the event is assessed as stable by the Investigator, the subject is lost to follow-up, or the subject withdraws consent. Every effort should be made to follow all SAEs considered related to study treatment or trial-related procedures until a final outcome can be reported.

All pregnancies reported during the study should be followed until pregnancy outcome. If the EDC system is not available at the time of pregnancy outcome, follow reporting instructions provided in Section 11.4.

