11.5.3. Post-study Adverse Events

At the treatment discontinuation visit, the Investigator should instruct each subject to report to the Investigator any subsequent AEs that the subject's personal physician believes could be related to prior study treatment or study procedures.

The Investigator should notify the Sponsor of any death, SAE, or other AE of concern occurring at any time after a subject has discontinued study participation if the event is believed to be related to prior study treatment or study procedures. The Sponsor should also be notified if the Investigator becomes aware of the development of cancer or a congenital anomaly/birth defect in a subsequently conceived offspring of a subject that participated in this study.

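### Section 11.4 sets a 28-day post-dose window for immediate pregnancy reporting but a 90-day window for contraception, so an uncomplicated pregnancy on days 29 to 90 has no clear immediate-reporting duty

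*Protocol*

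**What the plan says.** Protocol Section 11.4 contains two post-treatment windows.

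- **Reporting.** Known or suspected pregnancies of a female subject or of a male subject's partner, including a positive test, that occur on study treatment or within 28 days of the "last dose of study treatment, are considered immediately reportable events".
- **Contraception.** Women of reproductive potential, and fertile men whose partners are, must use two effective forms "throughout the study and for 90 days (both females and males) following the last dose of study drug". Men must also agree that they "will avoid conceiving for 90 days after the last dose of study treatment". Inclusion criterion 13, in the synopsis and in Section 8.2, repeats the 90 days.

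Section 11.4 also states that "Pregnancy is neither an AE nor an SAE, unless a complication relating to the pregnancy occurs". Further sentences there carry no time limit. They ask the investigator to document the course and outcome of all pregnancies, including after the subject or the study has finished, and to report pregnancy outcomes and any SAE during pregnancy.

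No reason is given for using 28 days in one place and 90 in the other.

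**The concern.** For 90 days after the last dose the protocol regards conception as something to prevent, in women and in men. For the last 62 of those days it does not clearly ask to be told if prevention fails. Failure is foreseeable: Section 9.13.4 warns that AG-120 may lower hormonal contraceptive concentrations, and Section 11.4 counts hormonal methods among the effective forms (though two forms are required, one of them a barrier).

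At stake is the completeness of the reproductive safety data. If only complicated or abnormal pregnancies come to notice after day 28, the sponsor has adverse outcomes without the number of pregnancies from which they arose.

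**Working it through.** The plan has no figure to reproduce. The check is the length of the gap, whether another rule closes it, and how much drug is present.

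**1. The gap.** Inputs: 28 days and 90 days, both from Section 11.4.

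- Uncovered days: 90 − 28 = 62 (days 29 to 90).
- Share of the contraception window: 62 / 90 = 0.689, or 69%.

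**2. Does any other rule close it?**

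| Protocol rule | Time limit after last dose | Covers an uncomplicated pregnancy on days 29–90? |
|---|---|---|
| 11.4, immediate reporting | 28 days | No |
| 11 and 11.2, AE and SAE reporting | 28 days for all events; afterwards related SAEs only | No: pregnancy alone is not an event |
| 11.4, course and outcome of all pregnancies | None stated | Unclear: the 28-day sentence may or may not set the scope |
| 11.4, SAEs during pregnancy | None stated | No: complications only |
| 11.5.1, "All pregnancies reported during the study should be followed until pregnancy outcome" | Depends on a report having been made | No: it creates no duty to report |
| 11.5.3, notice of "a congenital anomaly/birth defect in a subsequently conceived offspring of a subject that participated in this study", and of related events of concern | None, but the investigator must become aware | No: adverse outcomes only |

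No row gives a clear duty for an uncomplicated pregnancy in the gap, and the rows together do not yield a count of all pregnancies.

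**3. How much drug is present?** Section 5.3.3.1 gives mean half-lives of 38.4 to 86.2 hours. Assuming simple exponential decline, the fraction left at day 28 is 0.5^(28 × 24 / half-life), and 28 × 24 = 672 hours.

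- At 38.4 h: 672 / 38.4 = 17.5 half-lives; 0.5^17.5 = 0.0000054, about 0.0005%.
- At 86.2 h: 672 / 86.2 = 7.80 half-lives; 0.5^7.80 = 0.0045, about 0.45%.
- Five half-lives take 5 × 38.4 / 24 = 8.0 days to 5 × 86.2 / 24 = 18.0 days.

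A conception after day 28 therefore meets little circulating drug.

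**4. Conception or detection?** Section 11.4 does not say which of these dates a pregnancy. Table 3 schedules tests at Screening and on Day 1 of each cycle, with none at end of treatment or in follow-up. With 28-day cycles, a subject whose last dose falls on Day 28 had her last scheduled test 27 days earlier. A conception late in treatment could first be found after day 28. If detection sets the date, a site could treat that pregnancy as outside the window although it began on drug; if conception does, it is inside.

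**The case against.** The strongest reply is that the two windows do different jobs. Contraception is a precaution asked of subjects; immediate reporting is a duty on investigators, and its 28 days matches the protocol's general AE period. Nothing in the documents says the two must be equal. That stands: this is a mismatch that needs a reason or a reconciliation, not a logical contradiction.

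A reader might also infer that drug-exposed pregnancies in days 29 to 90 go wholly unrecorded and receive no outcome follow-up. The documents do not support that.

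- The half-life check leaves well under 1% of the drug at day 28, so these are pregnancies inside a precaution window, not evident exposures.
- The sentences in Section 11.4 on the outcome of all pregnancies and on SAEs during pregnancy have no stated limit and can be read as applying after day 28.
- Section 11.1.3 makes a birth defect in the infant of an exposed parent an SAE, related SAEs stay reportable without limit, and Section 11.5.3 asks for notice of birth defects in offspring conceived later, with no relatedness condition on that item.

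What remains is narrower. These routes depend on the investigator learning of an adverse outcome, or on reading the undated sentences broadly. None clearly brings in the uncomplicated pregnancies.

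It is also fair to say that 69% is a share of calendar days, not of expected cases.

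**Conclusion.** The point holds as a minor gap in safety-data collection. For 62 of the 90 days in which the protocol requires contraception, an uncomplicated pregnancy has no clear immediate-reporting duty, and the reach of the outcome-follow-up sentences is ambiguous.

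The number of pregnancies affected cannot be computed, because the documents give no expected age or sex distribution. It is likely to be small, with about 186 subjects with advanced cancer and assumed median survival of 8 to 12 months. It need not be zero: adults from 18 are eligible and partners of male subjects are included.

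No efficacy endpoint, power figure or error rate is touched. The SAP lists pregnancy test results (Section 9.4.6) and plans no summary of pregnancies. The residual-drug figures rest on the reported mean half-lives and simple exponential decline; individual subjects may differ. This review takes no view on whether 90 days is the right contraception period.

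**What to change.** Amend Section 11.4 in three places:

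1. Reconcile the two windows so that pregnancy reporting covers the whole period in which the protocol requires contraception. If the sponsor intends them to differ, state why.
2. State that the sentences on course, outcome and SAEs during pregnancy apply over that same period.
3. Say whether *occurring* refers to conception or to detection, so that a pregnancy begun on treatment and found later is handled the same way at every site.

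The cost is protocol wording and at most a few extra pregnancy reports. A reporting form already exists. Subjects are already contacted about every 12 weeks (84 days) after end of treatment, or seen every 6 weeks in PFS follow-up, so the question can be asked at existing contacts. No analysis changes.

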11.5. Follow-up of Subjects After Adverse Events

11.5.1. Investigator Follow-Up

The Investigator should follow each AE until the event has resolved to baseline grade or better, the event is assessed as stable by the Investigator, the subject is lost to follow-up, or the subject withdraws consent. Every effort should be made to follow all SAEs considered related to study treatment or trial-related procedures until a final outcome can be reported.

All pregnancies reported during the study should be followed until pregnancy outcome. If the EDC system is not available at the time of pregnancy outcome, follow reporting instructions provided in Section 11.4.

11.5.2. Sponsor Follow-up

For SAEs, AEs of special interest, and pregnancies, the Sponsor or a designee may follow-up by telephone, fax, electronic mail, and/or a monitoring visit to obtain additional case details and outcome information (eg, from hospital discharge summaries, consultant reports, autopsy reports) in order to perform an independent medical assessment of the reported case.

11.5.3. Post-study Adverse Events

At the treatment discontinuation visit, the Investigator should instruct each subject to report to the Investigator any subsequent AEs that the subject's personal physician believes could be related to prior study treatment or study procedures.

The Investigator should notify the Sponsor of any death, SAE, or other AE of concern occurring at any time after a subject has discontinued study participation if the event is believed to be related to prior study treatment or study procedures. The Sponsor should also be notified if the Investigator becomes aware of the development of cancer or a congenital anomaly/birth defect in a subsequently conceived offspring of a subject that participated in this study.

12. STATISTICAL METHODS

12.1. General Methods

Summaries will be produced for disposition, demographic and baseline disease characteristics, safety and tolerance, pharmacokinetics, PD biomarkers, and efficacy variables, as appropriate.

Categorical data will be summarized by frequency distributions (number and percentages of subjects). Continuous data will be summarized by descriptive statistics (mean, standard deviation, median, minimum, and maximum). Time-to-event endpoints will be estimated using Kaplan-Meier methods. Point estimates and 95% CIs will be provided where appropriate, and estimates of the median and other quantiles, as well as individual time points (eg, 3-month, 6-month, and 12-month rates) will be produced.

All data will be provided in by-subject listings.

The study data will be analyzed and reported in the primary clinical study report (CSR) based on all subjects' data up to the time when 131 PFS events have been determined by Investigator assessment. Any additional data for survival follow-up and for subjects continuing to receive study treatment past the data cutoff date for the CSR until the occurrence of 150 OS events will be reported at the end of the study in the final CSR.

12.2. Sample Size Estimation

A total of approximately 186 subjects will be needed for the study.

The primary objective of the study is to demonstrate the improvement in PFS by IRC assessment for subjects receiving treatment with AG-120 as compared to subjects receiving placebo. Assuming a hazard ratio (HR) of 0.5 for PFS (equivalent to a median PFS of 3 months in the placebo arm versus 6 months in the AG-120 arm, assuming an exponential distribution), a total of 131 PFS events are required to provide 96% power at a 1-sided alpha of 0.025 level of significance to reject the null hypothesis (Section 12.7.1) using a stratified log-rank test. Based on this, a total of approximately 186 subjects will need to be randomized in a 2:1 ratio to the AG-120 and placebo arms, respectively, assuming approximately a 22% dropout rate, an approximate 26-month randomization period, and an additional 6-month follow-up for PFS after the last subject is randomized. Therefore, the primary analysis of PFS will occur at approximately 6 months after the last subject is randomized.

Overall survival will be analyzed twice, once at the time of the final analysis for PFS and once at the occurrence of 150 OS events (final analysis for OS, which will occur at approximately 24 months after the last subject is randomized). Assuming an HR of 0.67 for OS (median OS of 8 months in the placebo arm vs. 12 months in the AG-120 arm, assuming an exponential distribution), a total of 150 OS events will provide 64% power at a 1-sided alpha of 0.025.

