Primary Endpoint Results and Subsequent Study Unblinding: Once the primary endpoint of PFS (based on central radiology RECIST 1.1 assessment) is statistically analyzed, the Sponsor will communicate the topline aggregate results of the study via public disclosure, which will include participating study teams. Shortly after public disclosure of the topline aggregate results, the Sponsor will communicate to all sites that treatment assignments of all subjects will be unblinded and will also inform sites which of the 2 following scenarios to pursue following unblinding.

If the primary endpoint is statistically positive, all ongoing subjects (AG-120 and placebo-treatment assigned subjects) will be given the opportunity to receive open-label AG-120 following unblinding. Unblinding will no longer be contingent upon documented radiographic disease progression. Subjects who were already receiving AG-120 may continue to receive AG-120 on the same assessment schedule. Subjects who were receiving placebo and continue to meet cross-over eligibility criteria will be given the opportunity to receive open-label AG-120. For subjects who cross over, placebo will not be counted as a prior line of therapy for the purpose of eligibility. If subjects cross over, they will follow the same assessment schedule as

from CID1. Prior to crossing over, these subjects will undergo a CT or MRI that will serve as the new baseline against which all subsequent RECIST v1.1 assessments will be performed. If the subject has undergone a recent CT or MRI (≤ 3 weeks prior to start of cross-over treatment), the scan does not need to be repeated. Palliative radiotherapy to treat symptomatic pre-existing or new non-target lesions (per RECIST v1.1) that cannot otherwise be medically managed will be permitted after unblinding has occurred. AG-120 should be held for the duration of palliative radiotherapy. A 2-week washout from completion of radiotherapy will be required prior to starting or resuming AG-120. For subjects receiving palliative radiotherapy prior to the first dose of open-label AG-120, a repeat CT or MRI will be performed upon completion of the 2-week washout period to document the area that was irradiated and to serve as the new baseline. All decisions to pursue palliative radiotherapy will require Sponsor and/or Medical Monitor approval.

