12.7.2. Analyses for the Secondary Efficacy Endpoints

12.7.2.1. Overall Survival

Overall survival is defined as the time from date of randomization to the date of death due to any cause. Subjects who are alive at the analysis cutoff date will be censored at the date of last contact.

Assuming an HR of 0.67 for OS (median OS of 8 months in the placebo arm vs. 12 months in the AG-120 arm, assuming an exponential distribution), a total of 150 OS events will provide 64% power at a 1-sided alpha of 0.025. With a sample size of 186, additional OS follow-up of approximately 24 months after last subject is randomized will be needed to obtain 150 OS events. Assuming an HR of 0.615 (median OS of 8 months in the placebo arm vs. 13 months in the AG-120 arm, assuming an exponential distribution), a total of 150 OS events will provide 80% power at a 1-sided alpha of 0.025.

Due to the allowance of cross over of subjects who progress on the placebo arm to the AG-120 arm, it is anticipated that the true effect of AG-120 on survival as compared to placebo will not be able to be measured, and that the trial will not be powered to detect a meaningful survival effect.

OS will be compared between the two treatment arms, provided the primary endpoint PFS is statistically significant favoring the AG-120 arm. A hierarchical testing procedure will be adopted in this study and the OS analyses will be performed only if the primary efficacy endpoint PFS is statistically significant. OS will be analyzed based on the data from the ITT, according to the treatment arm to which subjects were randomized and the strata they were assigned at randomization. The distribution function of OS will be estimated using the Kaplan-Meier method. The median OS along with 95% CIs will be presented by treatment arm.

Assuming a proportional hazards model for OS, the null hypothesis will be tested:

$$H_{02} \text{ (null hypotheses): } \Theta_2 \geq 0 \text{ vs. } H_{a2} \text{ (alternative hypotheses): } \Theta_2 < 0$$

where Θ_2 is the log hazard ratio of OS in the AG-120 (investigational treatment) arm vs. placebo (control) arm.

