8.3. Overall Survival (OS)

The OS analysis will be based on ITT set and will include all OS data, including data after crossover.

Overall survival is defined as the time in months from the randomization date to the date of death due to any cause. Subjects without documentation of death at the time of the data cutoff for analysis will be censored at the date the subject was last known to be alive, or the data cutoff date, whichever is earlier. The last known alive date is the last record in the study database. For example, this date may be the maximum of the last visit date or last contact date, including telephone follow-up where the subject is known to be alive.

As a primary analysis, a stratified one-sided log-rank test will be used to compare OS between the two treatment groups, with the one-sided significance level controlled at 0.025. The HR along with the 95% CI will be estimated using a stratified Cox model. For both the stratified log-rank test and the stratified Cox model, the strata will be those at randomization. A Kaplan-Meier plot for OS will be presented by treatment arm. Estimates and 95% CIs for the 25th percentile, median, and 75th percentile for OS will be presented by treatment arm (if estimable). Probabilities of survival at selected time points (3 months, 6 months, 9 months, and 12 months) may also be presented.

In addition, the following subgroup analyses will be performed:

- Subgroup analysis with unstratified log-rank test and unstratified Cox regression model. The HR (AG-120/placebo) with its 95% CI will be displayed for all subgroups graphically in a forest plot. The subgroups will include:
 - The actual number of prior line of therapies in advanced setting (1 vs. ≥ 2)
 - Gender (female vs. male)
 - Extent of disease at screening (locally advanced vs. metastatic)

- If subject had both locally advanced and metastatic, it would be considered as metastatic
- Intrahepatic vs. extrahepatic
 - Perihilar will be lumped into extrahepatic category
- ECOG at baseline (0 vs. ≥ 1)
- Regions (North America vs. Europe vs. Asia)

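### Is the 64% survival power misleading where it is stated without the crossover caveat of Protocol Section 12.7.2.1?

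*Protocol*

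**What the plan says.** Four places give the same power for overall survival (OS): the Protocol Synopsis (Statistical methods), Protocol Sections 12.2 and 12.7.2.1, and SAP Section 5. In the words of Section 12.2, "a total of 150 OS events will provide 64% power at a 1-sided alpha of 0.025". Each place ties the figure to an HR of 0.67, exponential survival, and medians of 8 months on placebo and 12 months on AG-120.

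Protocol Section 12.7.2.1 adds a second scenario: at an HR of 0.615 (8 against 13 months), "a total of 150 OS events will provide 80% power at a 1-sided alpha of 0.025". The next paragraph begins "Due to the allowance of cross over of subjects who progress on the placebo arm to the AG-120 arm" and concludes that the true survival effect is not expected to be measurable and that "the trial will not be powered to detect a meaningful survival effect". The Synopsis mentions crossover for OS only as a topic for sensitivity analyses. SAP Section 5 does not mention it.

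On the analysis, SAP Section 8.3 states: "The OS analysis will be based on ITT set and will include all OS data, including data after crossover". The same section and Appendix C plan a rank preserving structural failure time (RPSFT) model with re-censoring as a sensitivity analysis.

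OS is tested second in the fixed sequence, after progression-free survival (PFS) and before response rate. Section 12.7.2.1 adds that "the OS analyses will be performed only if the primary efficacy endpoint PFS is statistically significant". Protocol Section 7.1 says that after a positive PFS result "Unblinding will no longer be contingent upon documented radiographic disease progression", and then: "Subjects who were receiving placebo and continue to meet cross-over eligibility criteria will be given the opportunity to receive open-label AG-120".

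**The concern.** The power figures and the caveat appear to disagree. Three places promise 64% with no word on crossover, while a fourth gives 64% and 80% and then says the trial lacks power for survival. The figures show no crossover input, yet the confirmatory OS test keeps all follow-up after crossover, so it is exposed to exactly the dilution the caveat describes. The caveat names only placebo subjects who progress, although a positive PFS result, which the OS test requires, also opens AG-120 to placebo subjects who have not progressed. The documents also do not say whether the HR of 0.67 or the 8-month placebo median already allows for crossover.

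At stake is interpretation. Someone who reads only the Synopsis, Section 12.2 or the SAP could take a non-significant OS result as failure of a test with 64% power when the real power was lower. Because OS precedes response rate in the sequence, low OS power also affects whether response rate can be formally tested.

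**Working it through.** **1. Reproduce the stated figures.** Inputs from Protocol Sections 12.2 and 12.7.2.1: 150 deaths, 2:1 allocation, one-sided alpha 0.025 (critical value 1.960), HR 0.67 or 0.615. Schoenfeld's formula is

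power = Φ( √(d · p · (1 − p)) · |ln HR| − 1.960 ), with d = 150 and p = 2/3.

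√(150 × 2/3 × 1/3) = √33.33 = 5.774.

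- HR 0.67: 5.774 × 0.4005 = 2.312; 2.312 − 1.960 = 0.352; Φ = 63.8%. Stated: 64%.
- HR 8/12: 5.774 × 0.4055 = 2.341; 2.341 − 1.960 = 0.381; Φ = 64.8%.
- HR 0.615: 5.774 × 0.4861 = 2.807; 2.807 − 1.960 = 0.847; Φ = 80.1%. Stated: 80%.

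Both figures reproduce. Allowing for the OS interim look (gamma spending with parameter −8, taken at an assumed 95 to 125 deaths) gives 63.6% to 63.7%, a loss of about 0.2 points at most.

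**2. What the 64% claims.** In this formula power depends on the event count, the allocation and the HR that holds in the tested comparison. Crossover enters through that HR. So 64% is correct if the intention-to-treat HR is 0.67, and the caveat warns that crossover will stand in the way of seeing the drug's full effect. A conditional figure and a warning about its condition can both be true.

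**3. What dilution would do.** With the same formula and 150 deaths:

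| Intention-to-treat HR | Power |
|---|---|
| 0.67 | 64% |
| 0.70 | 54% |
| 0.75 | 38% |
| 0.80 | 25% |
| 0.85 | 15% |

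Moving from a crossing share to a diluted HR needs inputs the documents do not give. One simulation used the protocol's accrual (5 per month for 6 months, then 8), placebo medians of 3 months for PFS and 8 months for OS, an AG-120 OS median of 12 months, and no loss to follow-up. It assumed that crossover at progression multiplies the death hazard by 2/3. Power was 67% with no crossover, and 52%, 37%, 26% and 17% when 25%, 50%, 75% and 100% of placebo progressors crossed. Over a wider set of assumptions at HR 0.67 (25% to 90% crossing, hazard factor 0.67 or 0.8, equal or higher death hazard after progression), power ran from 10% to 58%. All of this holds only if the 8-month placebo median excludes crossover, which the documents do not state.

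**4. The second crossover route.** How many placebo subjects would still be progression-free at the PFS analysis, 6 months after the last randomization? The placebo PFS hazard is ln 2 / 3 = 0.231 per month. Accrual of 186 takes 6 months for the first 30 and 156/8 = 19.5 months for the rest. Follow-up at the analysis is therefore 6 to 25.5 months for the later group and 25.5 to 31.5 months for the first 30.

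- Later group: (8/0.231) × (e^(−0.231×6) − e^(−0.231×25.5)) = 34.6 × (0.2500 − 0.0028) = 8.56.
- First 30: (5/0.231) × (0.0028 − 0.0007) = 0.05.
- Share: 8.61/186 = 4.6%; of 62 placebo subjects, about 2.9.

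This route concerns about 3 subjects and adds little to the dilution from crossover at progression.

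**The case for a change.** The strongest case for a change is that the caveat appears once, in the protocol only. The SAP never carries it, and even Section 12.7.2.1 does not say whether its own 64% and 80% exclude crossover. If they do, a label is missing in four places. If the 8-month median already includes crossover, the caveat needs reconciling with the figures. Either way the repair costs only wording. RPSFT is a sensitivity analysis and gives no power back to the confirmatory test.

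The textual part of this stands: the caveat is missing from three places, and the basis of the assumed HRs is not stated. Two parts carry less weight. The gap over placebo subjects without progression is real but concerns about 3 of 62, and that route was added in Amendment 5, whereas the SAP is written to Amendment 4. The point about response rate is true of the testing order, but rewording a power statement would not alter the chance of reaching that test. Adding a range of powers by crossing share would put into the protocol numbers that rest on assumptions it does not contain.

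**Conclusion.** No change to the plan is needed. The 64% and 80% are correct for the HRs they name (63.8% and 80.1%), and every statement of the 64% gives its HR, medians and distribution. The protocol's own OS section says plainly that crossover undermines the comparison. The SAP keeps the intention-to-treat test as primary and plans an adjusted sensitivity analysis. The sample size rests on PFS and is unaffected.

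Actual OS power could fall well below 64% if 0.67 is a crossover-free HR: 38% at a diluted HR of 0.75, 25% at 0.80. Those values show direction rather than size, because the documents fix neither the crossing share nor the effect after crossover. Section 12.7.2.1 already gives that direction. A statistician interpreting a non-significant OS result would work from that section and from the observed crossover. Repeating the caveat elsewhere would be an editorial courtesy that alters no analysis, alpha, testing order or conclusion.
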